Title : Comparison of the diagnostic accuracy of Hysterosalpingo-lidocaine-foam sonography versus hysterosalpingography in tubal patency assessment to the gold standard of laparoscopy and dye testing

Date: 1/5/2022

NCT05419921

Faculty of Medicine, Cairo University Postgraduate Research Program Template

1- Study

Title :

Comparison of the diagnostic accuracy of Hysterosalpingo-lidocaine-foam sonography versus hysterosalpingography in tubal patency assessment to the gold standard of laparoscopy and dye testing

Degree: Date of registration: May 2022

2. Investigators :

1-[name] [name] & Gyn Cairo university
2-[name] Assisstant [name] & Gyn Cairo University
3-[name] Assistant Lecturer Obs & Gyn New Giza University
4-[name] Lecturer Obs & Gyn Cairo University
5-[name] Medical Student Cairo University

3. Investigators:

4. Background:

Tubal disease accounts for 30-40% of female factors of infertility.(1) Therefore, tubal testing is an essential part of female infertility work-up.(2,3) Since falsely occluded tubes may lead to unnecessary interventions and falsely patent tubes may lead to unsuccessful in-vitro fertilization embryo transfer (IVF-ET) trials,(5,6) an accurate tubal test is an essential.

laparoscopy with dye testing (LDT), i.e., laparoscopic chromopertubation, is the gold standard tubal patency test.(1,6,7) It is the recommended tubal test by the National Institute for Health and Clinical Excellence (NICE) and the European Society of Human Reproduction and Embryology (ESHRE) for women suspected to have tubal disease as it allows for direct visualization, diagnosis, and treatment of tubal and other pelvic pathologies.(3,8) However,

LDT is an invasive procedure requiring general anesthesia that can be associated with bleeding and visceral injury.(1,6,7,9)

Hysterosalpingogram (HSG) has been reported to have sensitivity of 53% and specificity of 87% in the diagnosis of tubal block.(4) It has been the most commonly used initial tubal patency test as it offers a less-invasive and less-expensive alternative to LDT.(6) However, HSG is associated with radiation exposure, pain, and allergy. It cannot diagnose myometrial or ovarian pathologies as well.(1,6,7,9)

Hysterosalpingo-contrast sonography (HyCoSy) was introduced as a safer and less-painful alternative to HSG with comparable diagnostic accuracy and superiority in diagnosing uterine, ovarian, and myometrial pathologies.(1,6,9,10-12) HyCoSy is the recommended tubal test by NICE for women not known to have tubal disease, as an alternative to HSG, whenever appropriate expertise is available.(3) Air and saline use as contrast medium with HyCoSy made the procedure highly operator dependent.(1,6,13-16) Hyperechogenic and longer-lasting echogenic media then followed but are currently commercially unavailable or not approved for tubal testing.(1,6,14– 19)

In 2007, ExEm gel (GynaecologIQ, Delft, Netherlands) was introduced(20) and registered as European Confirmatory (CE) approved drug for tubal testing.(15) Hysterosalpingo-foam sonography (HyFoSy), using diluted ExEm gel foam, has been established as a safe, feasible, tolerable, and accurate alternative to HyCoSy and HSG that has been widely used in infertility clinics.(1,6,7,9,10,14,18,19,21–26)

In 2017, hysterosalpingo-lidocaine-foam sonography combined with power doppler (HyLiFoSy-PD) was introduced as a cost effective and less painful possible alternative to HyFoSy that can be used whenever the contrast media is unavailable. "Flaming tube" sign, detected using power doppler (PD), was also described as to allow easier recognition of tubal patency.(27) Our study aims to compare the diagnostic accuracy of HyLiFoSy-PD with the most commonly used tubal test; HSG, with reference to the gold standard tubal test; laparoscopy and dye testing.

5. Objective:

The aim of this study is to evaluate the difference between the diagnostic accuracy of Hysterosalpingo-lidocaine-foam sonography and hysterosalpingography, with reference to the gold standard tubal test; laparoscopy with dye testing.

6. Study Design:

This will be a cross-sectional study

7. Scientific committee approval:

8. Study methodology:

Population of study, disease condition and setting:

Women in the reproductive age group between 18- and 40-years old presenting with primary or secondary infertility who underwent HSG in the previous 5 years as a part of their infertility work-up with availability of good-quality HSG images, & did not get pregnant in this period, and gave no history of incidences that might affect their tubes, such as : abdominal surgery or laparoscopy, pelvic inflammatory disease, smoking, and intrauterine device insertion.

Women fitting these inclusion criteria and scheduled for LDT as part of their infertility work up will be considered. HyLiFoSy-PD will be carried out few days before the already scheduled LDT.

The study will be conducted in the Cairo fetal medicine unit, department of Obstetrics and gynecology, Cairo university.

Inclusion criteria:

- 1. Age group (18-40)
- 2. Informed signed Written consent.
- 3. Scheduled for LDT as a part of their infertility management

- 4. Have undergone HSG in the previous 5 years with the availability of good-quality HSG images.
- 5. No incident factors that might have affected the tubal status after she underwent HSG within the previous 5 years, such as ; abdominal surgery or laparoscopy, pelvic inflammatory disease, smoking, and intrauterine device insertion.

Exclusion criteria:

Women with any of these factors will be excluded:

- 1. LDT scheduled for a therapeutic purpose due to a known tubal or ovarian pathology
- 2. Lack of good-quality HSG images.
- 3. Withdrawal of consent.
- 4. Using contraception
- 5. Women outside reproductive age
- 6. Known allergy to lidocaine
- 7. Active pelvic inflammatory disease
- 8. Undiagnosed genital tract bleeding.
- 9. Evident tubal pathology (such as hydrosalpinx) or pregnancy diagnosed by transvaginal ultrasound (TV-US) prior to performing HyLiFoSy-PD

Methodology in details

Interpretation of HSG results:

Review of the HSG films will be done for assessment of the tubal patency; tubes will be considered patent if the dye is seen throughout their whole length and till their ends with a positive immediate spill or a spill in the delayed film. If the dye does not pass through one or both cornual ends, or if a part of the tube is seen filled with dye but not the whole length then tubal obstruction will be considered. Patients with hydrosalpinx seen by HSG are to be assessed first by US if no visible hydrosalpinx is seen by US and she has no signs of PID then she can proceed to the HyLiFoSy-PD procedure.

Hysterosalpingo-lidocaine-foam sonography procedure:

- 1. HyLiFoSy-PD procedure will be performed in proliferative phase of the cycle (Days 5 12).
- Clinical evaluation including history taking and a baseline twodimensional (2D) TV-US examination will be carried out prior to starting the HyLiFoSy-PD procedure.
- 4. Administration of a non-Steroidal anti-inflammatory drug (NSAID) rectal suppository will be carried out one hour before the procedure (diclofenac sodium 100 mg), in addition to antibiotic prophylaxis using

oral azithromycin for 3 days, starting the day before the procedure and continued for one day afterwards

- 5. In the dorsal lithotomy position, the cervix will be visualized with a Cusco speculum, cleaned with an antiseptic, then a 5- or 6- Fr pediatric Foley's balloon catheter will be introduced into the cervical canal with the help of a Bozeman forceps and a tenaculum if necessary.
- 6. The balloon will be positioned in the lower uterine cavity and inflated with 2 ml of saline to prevent backflow of contrast medium through the cervix, then the speculum will be removed. The TV-US probe will be reintroduced in a longitudinal plane to confirm correct placement of the catheter.
- 7. The foam contrast agent will be created by mixing 3–4mL of 2% lidocaine gel (Xylocaine Jelly 2%, Atrazeneca, Sweden) with 16–17mL of saline. The assistant will create the foam immediately before application by shaking the mixture (approximately 10–20 times) between two connected syringes. This will be done until a whitish suspension is obtained.
- 8. Repeated small doses (3-5 ml) of the lidocaine-made foam will be infused slowly into the uterine cavity while observing the flow of the contrast medium in each fallopian tube.
- 9. Using greyscale US, flow over the whole length of the tube, fimbrial outflow, or peritoneal spillage of contrast will provide definite evidence

KASR ALAINY

of tubal patency. Contrast filling of the uterine cavity without cornual flow will suggest tubal occlusion.

- 10.PD will then be added to re-assess tubal patency and assess the "flaming tube" sign. Flaming sign interpretation will be classified as: strong, weak, or absent.
- 11.Images will be stored as 2D and PD still images and video clips.HyLiFoSy-PD will be performed by experienced sonographers at our unit, who will be blinded to the results of LDT.
- 12.Patients will be asked about the degree of discomfort or pain they felt during and immediately after the procedure. Using categorical verbal rating scale (VRS),(28) Procedure will be stopped if a patient experiences severe pain.
- 13.Patients will be followed up overnight and monitored for any other procedure-related side effects or complications.
- 14. Within a week following the HyLiFoSy-PD procedure, standard LDT will be carried out by experienced endoscopists who will be blinded to the results of HyLiFoSy-PD. During LDT, tubal patency will be tested using methylene blue dye. Tubal evaluation during LDT will be classified as: patent with immediate spill, patent with delayed spill, or blocked.

Possible Risk (mention if there is any risk or not)

Side effects such as vasovagal reactions, allergic reaction, and venous intravasation have been reported in literature in hysterosalpingo-foam studies. However, in our previous hysterosalpingo-lidocaine-foam sonography study, none of these side effects were encountered. For the possible risk of infection, all patients will be given prophylactic antibiotics. In addition, any case with visible hydrosalpinx or signs or symptoms of PID on US prior to performing HyLiFoSy-PD will not perform the procedure.

9. Study outcomes:

Primary outcomes

1. Diagnostic accuracy of HyLiFoSy and HSG with reference to LDT, in terms of sensitivity, specificity, positive predictive value, negative predictive value, and overall accuracy.

Secondary outcome parameters

1 -Diagnostic accuracy of adding power doppler to the HyLiFoSy.

2-Evaluate the procedure associated pain

3-Evaluate the procedure duration

4-Percentage of failed or inconclusive attempts and possible reasons for

that

5-Incidence and rate of potential complications for example: vasovagal and allergic reactions, venous intravasation.

10. Sample size: Using the following equation:(29)

$$N_{\text{Disease}} = \frac{\left\{z_{1-\alpha/2}\Lambda + z_{1-\beta}\sqrt{\Lambda^2 - \zeta^2(3+\Lambda)/4}\right\}^2}{\Lambda\zeta^2}$$

where $\Lambda = (1 - Se_1)Se_2 + (1 - Se_2)Se_1$ and $\zeta = (1 - Se_1)Se_2 - (1 - Se_2)Se_1$.

With power of the study 90%, CI 95%, average sensitivity of HSG is 0.55,(4) and sensitivity of HyLiFoSy-PD is 90%,(30), prevalence of tubal pathology is 30%,(1); 100 patients are required to fulfill the sample size. To compensate for any possible dropouts (5%), 5 more patients will be recruited. So, the total sample size will be 105.

11. Statistical analysis:

After recording and collecting the data, statistical analysis will be performed using the Statistical Package for the Social Sciences (SPSS, version 16.0, SPSS Inc, Chicago, Illinois, USA). Data will be statistically described in terms of mean and standard deviation if they were of normal distribution, and in terms of median and range if they were not normally distributed. Frequencies (number of cases) and percentages will be used when appropriate. Accuracy will be represented using the terms sensitivity, specificity, PPV, NPV, and overall accuracy. Testing the difference in the results of tests was done using

one-way analysis of variance (ANOVA) test. P-values less than 0.05 will be considered statistically significant.

12. Source of funding:

Self-funding

13.Time plan From 1/6/2022 – 1/6/2024 (2 years)

14.References:

- Optimal evaluation of the infertile female. Fertility and Sterility. 2006 Nov;86(5 SUPPL.).
- Fertility problems: assessment and treatment Clinical guideline [Internet]. 2013. Available from: www.nice.org.uk/guidance/cg156
- 5. Tsiami A, Chaimani A, Mavridis D, Siskou M, Assimakopoulos E, Sotiriadis A. Surgical treatment for hydrosalpinx prior to in-vitro

KASR ALAINY

Cairo University

fertilization embryo transfer: a network meta-analysis. Ultrasound Obstet Gynecol. 2016 Oct 1;48(4):434–45.

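### HSG may be up to 5 years older than the laparoscopy that scores it, HyLiFoSy at most a week older, and the analysis plan never looks at HSG age

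*Combined protocol and SAP*

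**What the plan says.** Section 5 sets the goal: "The aim of this study is to evaluate the difference between the diagnostic accuracy of Hysterosalpingo-lidocaine-foam sonography and hysterosalpingography", with LDT as the reference. Section 6 labels the design: "This will be a cross-sectional study".

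The timing of the two index tests is set in section 8:

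- HSG, inclusion criterion 4: "Have undergone HSG in the previous 5 years with the availability of good-quality HSG images". No shorter window appears elsewhere.
- HyLiFoSy, procedure step 14: "Within a week following the HyLiFoSy-PD procedure, standard LDT will be carried out by experienced endoscopists".

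Section 8 also guards against change after HSG. Inclusion criterion 5 requires "No incident factors that might have affected the tubal status after she underwent HSG within the previous 5 years". The population paragraph describes women who "did not get pregnant in this period, and gave no history of incidences that might affect their tubes". Active pelvic inflammatory disease is an exclusion, and so is tubal pathology evident on transvaginal ultrasound before HyLiFoSy.

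The primary outcome in section 9 scores both tests against LDT. Section 11 states: "Accuracy will be represented using the terms sensitivity, specificity, PPV, NPV, and overall accuracy". It adds one ANOVA for the difference between tests and a 0.05 threshold. Neither it nor any other section has a stratum, covariate, restricted analysis or sensitivity analysis by HSG age.

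**The concern.** The two tests are judged by the same LDT but from very different distances. HyLiFoSy sees the tube that the surgeon will see within days. HSG may have seen it years earlier. If a tube was open at HSG and closed before LDT without symptoms, HSG was right on its day and is still marked wrong. HyLiFoSy, done after the closure, carries almost none of this penalty.

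The error therefore has a direction for sensitivity: it lowers the HSG figure and widens the gap in favour of the new test. That gap is what the study sets out to estimate. As the analysis is written, a reader of the results could not tell how old the HSGs were or whether the gap varies with their age.

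**Working it through.** **Inputs from the documents**

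- HSG sensitivity 0.55, HyLiFoSy sensitivity 0.90, prevalence 30%, 100 women before dropout (section 10).
- HSG specificity 0.87, from the Background: "sensitivity of 53% and specificity of 87% in the diagnosis of tubal block". An open tube is then read as blocked with probability 1 − 0.87 = 0.13.

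**The plan's own figure**

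The section 10 formula has Λ = 0.45×0.90 + 0.10×0.55 = 0.46 and ζ = 0.405 − 0.055 = 0.35. With two-sided alpha 0.05 and 90% power it gives 30.8 blocked women. Divided by 0.30 this is 102.8 women, against 100 stated; 30 blocked women gives exactly 100. The difference is one of rounding and plays no part in this point. I use 0.30 × 100 = 30 blocked women.

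**Assumptions that are mine**

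- q is the share of LDT-blocked women whose closure came after HSG and left no history or visible sign. The documents give no value. I use 1%, 5%, 10% and 20% (0.3, 1.5, 3 and 6 of 30), with 20% as an illustrative upper end.
- One result per woman. Section 8 reads patency by tube and does not say how two tubes combine into one result.
- HyLiFoSy sensitivity is unaffected, given its interval of at most a week.
- The errors of the two tests are independent given tubal status at each test.

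**Effect at the planning values**

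Apparent HSG sensitivity = (1 − q)×0.55 + q×0.13. Gap = 0.90 − that value.

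| q | HSG sensitivity | Gap |
|---|---|---|
| 0 | 0.550 | 0.350 |
| 1% | 0.546 | 0.354 |
| 5% | 0.529 | 0.371 |
| 10% | 0.508 | 0.392 |
| 20% | 0.466 | 0.434 |

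**Effect if the two tests were equal**

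Suppose both were truly at 0.90, which is not the plan's value for HSG. The apparent gap is q×(0.90 − 0.13) = 0.77q. The discordant probabilities are:

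- HyLiFoSy right, HSG wrong: b = (1 − q)×0.9×0.1 + q×0.9×0.87
- HSG right, HyLiFoSy wrong: c = (1 − q)×0.1×0.9 + q×0.1×0.13

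With 30 women, the chance of two-sided p < 0.05 in favour of HyLiFoSy is:

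| q | Apparent gap (points) | Exact McNemar | Asymptotic McNemar |
|---|---|---|---|
| 0 | 0 | 0.5% | 2.4% |
| 1% | 0.8 | 0.7% | 3.0% |
| 5% | 3.9 | 2.2% | 6.0% |
| 10% | 7.7 | 6.0% | 11.9% |
| 20% | 15.4 | 21.9% | 31.3% |

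The nominal level is 2.5% in this direction. McNemar's test serves as an illustration for paired results; section 11 does not name it.

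**Precision of a restricted analysis**

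Wilson 95% intervals for HSG sensitivity 0.55, and Newcombe paired 95% intervals for the gap 0.35 (b = 0.90×0.45 = 0.405, c = 0.10×0.55 = 0.055). The numbers with a recent HSG, 15 or 10, are assumed.

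| Blocked women | HSG sensitivity | Gap |
|---|---|---|
| 30 (all) | 0.377 to 0.712 | 0.125 to 0.535 |
| 15 | 0.315 to 0.765 | 0.028 to 0.597 |
| 10 | 0.274 to 0.799 | −0.043 to 0.638 |

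**The case against.** The best defence is that the protocol saw this problem and designed against it. Inclusion criterion 5 is aimed at change after HSG, and the no-pregnancy condition, the active-disease exclusion and the pre-procedure ultrasound add to it. What is left is closure with no reported cause and no visible sign, and nothing in the documents says that this is common. At the plan's own sensitivities, closure in 1% to 5% of blocked women moves the gap only from 0.35 to between 0.354 and 0.371. The most striking figures need 20% silent closure together with an HSG sensitivity of 0.90, far above the 0.53 and 0.55 that the documents cite.

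Most of that stands, and it keeps the point modest. It does not remove it. The safeguards rest on history or on what ultrasound can show. The no-pregnancy condition does not help against silent closure, since a woman whose tubes had closed would not be expected to conceive either.

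The woman-level calculation is also open to challenge. If one tube was already blocked, closure of the other may not change her result, depending on how a woman is classified. The table is therefore an illustration under a stated assumption.

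Finally, a restricted analysis of 15 or so blocked women cannot measure a shift of 0.004 to 0.084. That is correct, and it is the reason to keep the analysis descriptive.

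**Conclusion.** The point holds as a modest one. The unequal intervals, the common reference and the absence of any analysis by HSG age are all plain in the text. The direction for sensitivity follows from them: silent closure favours HyLiFoSy. The size is unknown. Over the assumed range of 1% to 20%, HSG sensitivity would be understated by 0.004 to 0.084, given 30 blocked women, one result per woman and an HSG specificity of 0.87.

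Three stronger readings are tempting, and the documents support none of them.

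- A reader might infer that every new closure is charged to HSG. It is not: HSG may already have read the tube as blocked (probability 0.13 here), and closures with pathology evident on ultrasound leave the study.
- A reader might infer that HSG age explains the planned difference. Even 20% silent closure adds only 0.084 to a planned gap of 0.35.
- A reader might take some closure rate, such as 5%, as a threshold below which the effect can be ignored. At 5% the chance of false significance is 2.2% with the exact test and 6.0% with the asymptotic one, and the plan names neither, so no such threshold can be drawn.

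**What to change.** Three additions to sections 8 and 11, all before data are seen:

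1. Keep the HSG date in the data set and report the distribution of the HSG-to-LDT interval.
2. Pre-specify a descriptive sensitivity analysis of the paired HSG–HyLiFoSy comparison restricted to recent HSGs, with the cut-off fixed in advance (12 months would be one example; the documents give no basis for a particular value). Report HSG sensitivity and specificity by interval with 95% confidence intervals, and no interaction test.
3. Word the main conclusion as a comparison with HSG done up to 5 years before LDT, not with a contemporaneous HSG.

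The cost is small. The date is already needed to apply inclusion criterion 4, and the rest is wording and one extra table. Eligibility and sample size stay as they are. The price is imprecision: if the restricted and full analyses look alike, the report should say that this does not rule out an effect of HSG age.

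### The unit of analysis is not fixed: the HSG, HyLiFoSy and laparoscopy reading rules are not aligned by side, and scoring per woman or per tube each has an unaddressed problem

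*Combined protocol and SAP*

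**What the plan says.** - **HSG** (section 8, Interpretation of HSG results): "If the dye does not pass through one or both cornual ends", or if a tube fills only in part, the reading is obstruction. The sentence names no side and does not separate one-sided from two-sided failure. The patency half of the rule speaks of tubes in the plural.
- **HyLiFoSy** (section 8, HyLiFoSy procedure): step 8 has the operator "observing the flow of the contrast medium in each fallopian tube". The occlusion criterion in step 9, absence of cornual flow, names no side.
- **LDT** (section 8, step 14): "Tubal evaluation during LDT will be classified as" immediate spill, delayed spill or blocked. It does not say whether this is per tube, per side or per woman.
- **Primary outcome** (section 9): sensitivity, specificity, predictive values and overall accuracy of both index tests against LDT, with no unit.
- **Sample size** (section 10): "100 patients are required to fulfill the sample size". The inputs are "average sensitivity of HSG is 0.55" and "sensitivity of HyLiFoSy-PD is 90" per cent, again with no unit.
- **Analysis** (section 11): the only comparative test is one-way ANOVA, and "P-values less than 0.05 will be considered statistically significant". Side matching and within-woman correlation are not mentioned.

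**The concern.** Each woman normally contributes two tubes, and each tube has three readings. The 2×2 tables behind the primary outcome cannot be built until the plan says what one entry in them is. Two routes are open, and each has its own problem.

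- **Per woman, any obstruction counts as positive.** An HSG call on the right in a woman whose LDT block is on the left counts as a true positive, although it is wrong about both tubes. The less specific test makes more such calls and so gains more credit, which distorts the HSG versus HyLiFoSy comparison.
- **Per tube, with no allowance for the woman.** Two tubes from one woman are treated as independent, and precision is overstated.

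These are alternatives, since only one applies once the unit is chosen. Leaving the choice open also allows it to be made after the results are seen. Section 4 motivates the study by the harm from falsely occluded and falsely patent tubes, so being right about the particular tube matters.

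**Working it through.** **The plan's own figure.** Inputs from section 10: Se1 = 0.55, Se2 = 0.90, two-sided alpha 0.05, power 90%, prevalence 30%.

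- Λ = 0.45 × 0.90 + 0.10 × 0.55 = 0.46; ζ = 0.405 − 0.055 = 0.35.
- The printed formula gives N_Disease = 30.83.
- 30.83 / 0.30 = 102.8, so 103 against the stated 100. Cutting 30.83 to 30 gives exactly 100, with power 89.0%.

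The figure reproduces closely as diseased subjects divided by prevalence. It contains no tube-level or clustering term.

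**Route 1: per woman, no side matching.** Inputs: HSG sensitivity 0.55 (section 10); HSG specificity 0.87 (section 4, where it is paired with a sensitivity of 53%); HyLiFoSy sensitivity 0.90 (section 10). Assumptions: all are per-tube values, errors in the two tubes are independent, and HyLiFoSy specificity, which the documents do not give, is 0.90.

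In a woman with one blocked tube, P(any flag) = 1 − (1 − Se) × Sp.

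| | Side-matched | Any flag | Wrong-side credit (1 − Se)(1 − Sp) |
|---|---|---|---|
| HSG | 0.55 | 1 − 0.45 × 0.87 = 0.6085 | 0.45 × 0.13 = 0.0585 |
| HyLiFoSy | 0.90 | 1 − 0.10 × 0.90 = 0.91 | 0.10 × 0.10 = 0.01 |
| Gap | 0.35 | 0.3015 | |

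If HyLiFoSy specificity is varied from 0.87 to 0.95, its any-flag sensitivity is 0.913 to 0.905 and the gap is 0.3045 to 0.2965. With the section 4 value of 0.53 for HSG, the any-flag figure is 1 − 0.47 × 0.87 = 0.591, of which 0.061 is wrong-side credit.

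The unit also moves specificity. A woman with two patent tubes is called clear by HSG with probability 0.87² = 0.757 if tube errors are independent. With correlation ρ this is 0.757 + ρ × 0.87 × 0.13, or about 0.79–0.81 for ρ = 0.3–0.5.

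**Route 2: per tube, woman ignored.** Let b be the share of tubes in the calculation whose partner is also in it, and ρ the within-woman correlation (assumed 0.3–0.5). The design effect is DE = 1 + bρ, the naive standard error is too small by 1 − 1/√DE, and a z-type test at nominal 5% has type I error 2 × [1 − Φ(1.96/√DE)].

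| b | DE | Naive SE too small by | Type I error |
|---|---|---|---|
| 0 | 1.0 | 0% | 5% |
| 0.5 | 1.15–1.25 | 7–11% | 6.8–8.0% |
| 1 | 1.3–1.5 | 12–18% | 8.6–11.0% |

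Sensitivity uses only LDT-blocked tubes, so b depends on how often both tubes are blocked, which the documents do not state. The b = 1 row is an upper bound for sensitivity.

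**The case against.** The strongest reply is that the rules are loosely worded rather than contradictory. The HSG rule also uses tube wording, both in its patency half and for partial filling, so the phrase about cornual ends may only describe laterality. A competent reader would record right and left anyway. HSG images are an entry requirement and HyLiFoSy images and clips are stored, so side could be recovered later for both index tests.

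Much of this stands. A reader might infer that HSG is read per woman while HyLiFoSy and LDT are read per tube; the documents do not say so. The HSG wording is mixed and the HyLiFoSy occlusion criterion names no side. Per-tube LDT is an inference, though a strong one, because a woman with one patent and one blocked tube fits none of the three categories. Recovery by re-reading does not extend to LDT, for which no stored images are mentioned. Nor does re-reading settle which unit is primary.

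Two objections to the arithmetic also stand. The unit of 0.55, 0.87 and 0.90 is unstated; if they are already per-woman values, the Route 1 figures fall away. And the type I error is for a z-type test, not the planned unpaired ANOVA. That test also ignores that both index tests are done in the same women, which makes it conservative if their results are positively correlated. It cannot be said that p-values under this plan would be too small overall.

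**Conclusion.** The concern holds as a gap in the plan: the three reading rules are not aligned on a unit, and no section supplies side matching or allows for two tubes per woman.

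Under the stated assumptions, per-woman scoring without side matching adds about 6 points to HSG sensitivity in one-sided disease and about 1 point to HyLiFoSy, narrowing the gap from 0.35 to about 0.30. Per-tube scoring that ignores the woman leaves the type I error of a z-type test anywhere from 5%, when no woman has both tubes in the analysis, to about 9–11%, when every woman does. The net direction under the planned ANOVA is unknown.

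A reader might also infer that 100 women are too few. The documents do not support that. The stated figure reproduces closely from its own inputs. A larger requirement would follow only from treating those inputs as per-tube values and converting them to per-woman ones. What is unclear is the unit of the inputs.

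**What to change.** 1. Reword the HSG rule so that it gives a result for each tube.
2. Record right and left separately for HSG, HyLiFoSy and LDT, with the LDT side entered at surgery.
3. State the primary unit before analysis and match all three tests by side.
4. If the woman is primary, as section 10 counts, a woman is LDT-positive when at least one tube is blocked. An index test is then a true positive only if it flags a tube that LDT shows blocked.
5. Also report side-matched tube-level sensitivity and specificity. The woman-level rule alone would leave false flags on the patent tube of a one-sided case uncounted.
6. For tube-level results, cluster both the standard errors and the HSG versus HyLiFoSy comparison by woman, using GEE or a bootstrap that resamples women.
7. State in section 10 whether the sensitivities and the prevalence refer to women or tubes.

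The cost is a few more form fields, slightly more analysis work and somewhat wider tube-level intervals. No extra patients or procedures follow from this point.

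### Must the HyLiFoSy reading rule be rewritten because it gives no class for partial filling and differs from the HSG rule on spill?

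*Combined protocol and SAP*

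**What the plan says.** All reading rules are in section 8 of the combined protocol and SAP.

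- **HyLiFoSy, greyscale (steps 8 and 9).** The operator infuses foam while "observing the flow of the contrast medium in each fallopian tube". Any one of three signs is enough for patency: "flow over the whole length of the tube, fimbrial outflow, or peritoneal spillage of contrast will provide definite evidence". The only sign of occlusion named is this: "Contrast filling of the uterine cavity without cornual flow will suggest tubal occlusion".
- **HyLiFoSy, power Doppler (step 10).** "PD will then be added to re-assess tubal patency", and the flaming tube sign is graded: "Flaming sign interpretation will be classified as: strong, weak, or absent". The Background says of this sign that it "was also described as to allow easier recognition of tubal patency".
- **HSG (Interpretation of HSG results).** The rule is that "tubes will be considered patent if the dye is seen throughout their whole length and till their ends with a positive immediate spill", or with spill on the delayed film. Failure to pass the cornu, or filling of only part of the tube, is obstruction.
- **LDT (step 14).** There are two patent classes, separated by the timing of spill, and a blocked class.

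The Objective (section 5) is to "evaluate the difference between the diagnostic accuracy of Hysterosalpingo-lidocaine-foam sonography and hysterosalpingography", with LDT as reference. Section 9 makes sensitivity, specificity, predictive values and overall accuracy of both tests the primary outcome. The accuracy of adding Doppler and the percentage of failed or inconclusive attempts are secondary outcomes. Section 11 does not say how inconclusive readings enter the accuracy measures.

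**The concern.** Accuracy against a reference needs every reading to be assigned, and step 9 does not cover every reading. Three things look wrong.

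1. **Partial filling.** The protocol names this pattern for HSG and calls it obstruction, but is silent for HyLiFoSy. If such tubes dropped out of the HyLiFoSy table and stayed in the HSG table, the two tests would be compared on different tubes.
2. **Whole-length flow without spill.** The three signs are alternatives, so this is patent on HyLiFoSy. HSG patency also needs spill, and both LDT patent classes are defined by spill. A distal block could be missed by HyLiFoSy because of its reading rule.
3. **Doppler.** No cut-off turns the three grades of the flaming sign into patent or blocked, so Doppler does not visibly settle the first two points.

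The stake is HyLiFoSy sensitivity, on which the sample size rests (0.90 against 0.55 for HSG). With about 30 blocked cases expected, a few unassigned readings could shift the estimate by several points.

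**Working it through.** **The plan's own figure.** Inputs from section 10: HSG sensitivity 0.55, HyLiFoSy-PD sensitivity 0.90, power 90%, two-sided 5% level, prevalence 30%.

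- Λ = 0.45 × 0.90 + 0.10 × 0.55 = 0.46
- ζ = 0.45 × 0.90 − 0.10 × 0.55 = 0.35
- The section 10 formula gives 30.83 diseased cases, and 30.83 / 0.30 = 102.8, so 103 women. The plan states 100, which is what 30 diseased cases would give (30 / 0.30). The figure is reproduced closely enough.

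**The rules side by side.**

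| Pattern seen on the index test | HyLiFoSy, step 9 | HSG |
|---|---|---|
| Nothing passes the cornu | suggests occlusion | obstruction |
| Passes the cornu, stops part-way | none of the three patency signs; no class stated | obstruction |
| Whole length, no spill seen | patent | fails the patency rule; not listed as obstruction |
| Whole length with spill | patent | patent |

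Each rule leaves one cell open: partial filling for HyLiFoSy, and whole-length filling without spill for HSG.

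**Partial filling: effect of the choice.** Assume the woman is the unit, with 30 blocked women (100 × 0.30), 27 of them detected (0.90). Let 3 of the 27 show partial filling. The documents give neither the unit nor this count, and 0.90 is stated for HyLiFoSy-PD, so all three are assumptions.

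- Called blocked: 27/30 = 0.900
- Left out: 24/27 = 0.889
- Read as patent, or counted as errors: 24/30 = 0.800

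Per tube, assuming 60 blocked tubes with 54 detected and again 3 affected: 54/60 = 0.900, 51/57 = 0.895 and 51/60 = 0.850.

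The starting point matters. If 0.90 is instead the sensitivity among blocked cases without partial filling, and 10% of blocked cases show it:

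- Called blocked: 0.90 × 0.90 + 0.10 = 0.91
- Left out: 0.90
- Read as patent: 0.90 × 0.90 = 0.81

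Under both set-ups, calling these cases blocked and leaving them out differ by about one point or less. Only the third choice moves the result materially.

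**Whole-length flow without spill: direction.** Take blockage as the target and compare reading such a tube as patent with reading it as blocked.

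- If LDT finds it blocked, the patent reading is a false negative, so sensitivity falls.
- If LDT finds it patent, the patent reading is correct, so specificity rises.

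The rule can therefore only lower HyLiFoSy sensitivity or leave it unchanged. On the measure that sized the study it cannot flatter the new test.

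**The case for a change.** The strongest case for a change is that the gap lies in the primary outcome, the protocol did close it for HSG, and closing it for HyLiFoSy would cost a sentence. Under the section 10 formula with HSG held at 0.55, a HyLiFoSy sensitivity of 0.85 would need about 154 women and 0.80 about 237, against 103 at 0.90. With 30 diseased cases, power would be about 71% or 52% instead of about 89%. On that view an unstated choice about a few cases could undo the planned power.

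Parts of this stand. Step 9 has no class for partial filling, the HSG rule has none for whole-length filling without spill, and no rule places inconclusive readings. Writing these down would be good practice.

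The rest is weaker.

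- The falls to 0.80 or 0.85 arise only if partial filling is read as patent, although none of the patency signs is present, or if a convention of counting inconclusive readings as errors is adopted. The plan states neither.
- Secondary outcome 4 already provides for inconclusive attempts. HyLiFoSy is done before LDT by sonographers blinded to its result (steps 11 and 14), so the reader cannot fit the class to the reference.
- Two index tests may use different positivity criteria. A test includes its reading rule, and a block missed under step 9 is a real error that LDT will expose.
- Women with hydrosalpinx on HSG but none visible on ultrasound may proceed, so distal blocks can enter. However, hydrosalpinx visible on ultrasound is excluded (exclusion 9), and exclusion 1 may remove some of the others.
- Step 10 sets two tasks, re-assessing patency and grading the flaming sign. The missing cut-off concerns the grade, and does not show that there is no Doppler patency reading. The accuracy of adding Doppler is a secondary outcome.
- Re-reading both tests under a common spill-based rule would be an optional extra. Nothing shows that stored clips, or HSG images up to five years old, would record spill or its absence for every tube.

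**Conclusion.** No change to the plan follows. What remains is a short list of definitions not written down: the HyLiFoSy class for partial filling, the HSG class for whole-length filling without spill, the Doppler cut-off, the handling of inconclusive readings and the unit of analysis. None of the stated rules is shown to give a wrong result. The different spill requirement is a property of the two tests and, on sensitivity, can only count against HyLiFoSy.

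The numerical effect is unknown, because the documents do not give the frequency of either pattern. In the illustration with three affected cases, the natural choices differ by 1.1 points per woman (0.900 against 0.889) or 0.5 points per tube (0.900 against 0.895).

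This conclusion rests on readers treating a tube with none of the three patency signs as blocked or inconclusive. It would weaken if such tubes were in practice called patent, or if they were dropped for HyLiFoSy and kept for HSG. The text points to neither.
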